- vii) Lives within 2 hours driving distance from Toronto up to London, Ontario OR willing to travel to either HB or TVCC for first in-person coaching session if randomized into coaching group

Child exclusion criteria:

- i) Surgery in past 6 months or upcoming 12 months that may impact PA or dietary intake (e.g. orthopedic surgery or neurosurgery)
- ii) Medical condition severely restricting diet
- iii) Underweight (less than fifth percentile)
- iv) Receiving specialist dietetic services

Parent inclusion criteria:

- i) Primary caregiver to a study participant
- viii) Can communicate in English and respond to questions requiring some reflection and insight

Sample size

Feasibility studies do not assess intervention efficacy and therefore do not require formal sample size calculations [33, 85]. The sample size ($n=30$) was set as a minimum needed to assess the key feasibility issues, as per feasibility best practices [86]. Fifteen SFC-Peds participants will suffice to show

Children and Teens in Charge of their Health: A feasibility study of solution-focused coaching to foster healthy lifestyles in children and young people with physical disabilities.

a tendency ($p < 0.10$) within the intervention group of behavioural change assessed by Goal Attainment Scaling (GAS; see ‘Outcomes’), equal to an effect size of 0.55 with a power of 0.80. The responsiveness of the secondary outcome measures will be compared with goal scores for evidence of concordance, e.g. a tendency of correlation between behavioural change and the Arc’s Self-Determination Scale. *Post hoc* estimates of variance will be key for the full trial’s design as they will inform the power calculations of the eventual RCT [85]. The sample size will allow us to assess recruitment success and show whether testing procedures, coaching goals and follow-up sessions are consistent across groups, mobility levels and sites. This sample size will also provide sufficient data for the qualitative work we are proposing to explore acceptability [87, 88].

Recruitment

We will recruit 15 children with SB and 15 children with CP (a total of 30 participants) and their parents from Holland Bloorview and TVCC.

Recruitment at Holland Bloorview

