Coaching will be guided by a framework developed by SFC-Peds clinicians at Holland Bloorview to integrate the Canadian Occupational Performance Measure (COM) and Goal Attainment Scaling (GAS) outcome measures into SFC-Peds (see Appendix 8 for framework). The **first coaching session** will take place in the family's home to establish rapport. Parents play an important supportive role in the coaching process, although the level and type of support they provide will be customized to the age and abilities of their child. SFC-Peds is ideal for establishing 'common ground' between children and parents so that they are working towards goals that they both deem important, maximizing the chances of sustainability. To enhance child self-determination, the coach will first support the child to identify their 'preferred future,' i.e. the 'big picture' the participant wants to work towards in the context of health habits. Then, the child, parent and coach will co-create actionable goals to help children to work towards it. Focusing upon goals that are personally meaningful to the child fosters autonomy [94]. The coach and parents will then support the child to identify realistic, real-world goal attainment strategies using their own strengths and resources, supporting the development of competence. The use of active listening, empathy and attentive body language creates a trusting relationship, and promotes a sense of relatedness [95]. Parental involvement in the coaching sessions will ensure that goals and goal-attainment strategies are realistic for the child, his/her environmental settings and the family. For example, if the parent cannot transport a child to an organized activity to meet their physical activity goal, then a different strategy would be co-created that is appropriate for the

Children and Teens in Charge of their Health: A feasibility study of solution-focused coaching to foster healthy lifestyles in children and young people with physical disabilities.

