Time 4 (SFC-Peds group): Children and their parents in the SFC-Peds group will undertake separate in-depth interviews facilitated by a qualitative interviewer to explore their experiences after coaching completion, perceived impact of intervention, barriers/facilitators to maintaining PA and dietary habits, and any unmet needs (see Appendix 16 for interview guide). Children will be asked to select 6-8 of their photographs taken since Time 2 to share with the interviewer. This will help remind children of their lifestyles in the previous six months, and enable them to speak in more depth about their feelings and experiences [106]. Each child will first be asked to explain why he/she took the photo, its meaning, what it shows of his/her coaching experience and the time since it ended.

Survey Time 4 (Control group only)

Time 4 (Control group): Children in the control group ($n=15$) will complete a Time 4 survey (see Appendix 17) regarding what they liked most/least about the study, any changes in health habits in the previous 12 months, acceptability of not getting the intervention, and tolerance of assessment protocols [30].

Qualitative Interview (Coaches only)

Time 4 (Coaches): Coaches will be interviewed to explore their experiences of delivering the intervention, e.g. challenges/facilitators, optimal coaching doses, use of technology (see Appendix 18).

Children and Teens in Charge of their Health: A feasibility study of solution-focused coaching to foster healthy lifestyles in children and young people with physical disabilities.

SECONDARY OBJECTIVE: *To determine the responsiveness of outcome measures to SFC-Peds coaching over 12 months.*

The following measures (excluding gender and date of birth) will be administered at Times 1, 2, 3, and 4 for all participants (approximately 1.5 hours duration). Issue identification and goal attainment measures are administered to SFC-Peds participants only with the first assessment conducted during the first coaching session. Measures have been selected based upon evidence of their responsiveness to change and psychometric properties in previous health promotion interventions [18]. Parent and child report questionnaires may be completed at home or online if the family prefers.

Participant characteristics

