DEMOGRAPHICS: Gender, date of birth, ethnicity, diagnoses, medications, current sports involvement (see Appendix 19 for demographics form). Questions from the International Study of Childhood Obesity, Lifestyle and the Environment survey (see Appendix 20) about the child's environment (e.g. accessibility of play areas) will also be collected [107].

FUNCTIONAL MOBILITY: The six-minute walk test for walkers [108] and the six-minute push test for non-walkers [109] (see Appendix 21).

Primary outcome measure

ISSUE IDENTIFICATION AND GOAL ATTAINMENT (CHILD REPORT):

Within-group change will be assessed using the Canadian Occupational Performance Measure (COPM) (see Appendix 22), which identifies the person-centred goal performance issues to improve, and assesses changes in occupational performance and satisfaction. Participant goal attainment will be assessed using Goal Attainment Scaling (GAS) (see Appendix 23), by defining five levels of goal attainment, thus ensuring that all attainment levels are mutually exclusive and measurable. This is an

Children and Teens in Charge of their Health: A feasibility study of solution-focused coaching to foster healthy lifestyles in children and young people with physical disabilities.

objective measure of behaviour change [110]. To minimize bias, GAS and COPM re-assessment will be conducted by a coach who has not worked with the child.

Secondary outcomes measures:

Between group change will be examined using the following measures:

BEHAVIOURAL ASSESSMENTS (CHILD REPORT):

Physical activity: The Habitual Activity Estimation Scale [111] (see Appendix 24) estimates time spent inactive, somewhat inactive, somewhat active, and very active, and shows good correlation with moderate to vigorous PA measured by accelerometry in our population ($p=0.02$) [112, 113].

Diet: The Dietary Screener Questionnaire (see Appendix 25) assesses dietary intake over the past 30 days and is validated against 24 hour multiple recall [114].

PSYCHOSOCIAL ASSESSMENTS (CHILD REPORT):

Self-determination: The *Arc's Self-Determination Scale* (see Appendix 26) has excellent reliability/validity with children with disabilities [64] and will assess self-determination to provide insight into potential mechanisms of behaviour change.

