SECONDARY OBJECTIVE: Measure responsiveness will be established by pre-post intervention differences using effect sizes (Cohen's *d*) and confidence intervals both within and between groups. It is well accepted to examine mean score changes for clinically significant differences pre and post intervention without calculating statistical significance (e.g. a score change of at least 2 points on the COPM is considered clinically significant [38]). We will therefore be able to assess the potential value of SFC-Peds over receiving printed materials only by examining goal scores over time. Our secondary outcomes will be compared with objective behaviour change (goal attainment) for concordance (e.g. whether successful goal attainment corresponds with increased self-determination). We will examine differences in outcome measures by disability, functional mobility, gender and age.

CHALLENGES

Our intervention (SFC-Peds) is largely virtual to reduce burden and enhance adherence [43]. All participants will receive gift cards for completing assessments to reduce attrition; this is a key feasibility outcome, especially in the control group. To reduce possible biases, participants will not meet during the study and coaches will not be involved in standard care. Standardized training (by 3 certified coaches) will be provided. Assessors will be asked which group they think participants are in; blinding success is indicated by accuracies at or below chance level. If adaptations are needed for the RCT, 'A process for Decision making after Pilot and feasibility Trials' (ADePT) [124] will be followed.

KNOWLEDGE TRANSLATION (KT)

A KT planning template [40] will ensure our findings have maximum reach yet are appropriate for feasibility study outcomes. The plan capitalizes on close collaboration of knowledge users and researchers within our investigative team. Integrated KT is promoted throughout the project by the involvement of clinical, family and knowledge user stakeholders, to ensure that the outputs meet the needs of the end users [125]. Holland Bloorview Research Family Engagement Committee members

Children and Teens in Charge of their Health: A feasibility study of solution-focused coaching to foster healthy lifestyles in children and young people with physical disabilities.

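### Goal scores are taken only in the coached arm, so they cannot show the value of SFC-Peds over printed materials

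*Combined protocol and SAP*

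**What the plan says.** The plan's statements on goal scores, by section:

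- **Design.** There are 15 children per arm. Both arms receive the printed materials, and the control arm receives nothing further beyond standard care. The stated purpose of the control arm includes accounting for information, maturation and repeated testing.
- **Study Assessments, Secondary Objective.** Measures are taken at Times 1 to 4 in everyone, but the next sentence makes an exception: "Issue identification and goal attainment measures are administered to SFC-Peds participants only with the first assessment conducted during the first coaching session".
- **Intervention implementation.** In that first session, "the child, parent and coach will co-create actionable goals".
- **Sample size.** The power statement concerns change "within the intervention group of behavioural change assessed by Goal Attainment Scaling".
- **Primary outcome measure.** COPM is assigned to within-group change, and GAS sits under the same heading.
- **Secondary outcomes measures.** A separate list follows: "Between group change will be examined using the following measures". It covers activity, diet, self-determination, self-efficacy, body composition and family habits.
- **Data Analyses, Secondary Objective.** Responsiveness is to be shown by Cohen's d and "confidence intervals both within and between groups". The plan then notes that "a score change of at least 2 points on the COPM is considered clinically significant", and concludes: "We will therefore be able to assess the potential value of SFC-Peds over receiving printed materials only by examining goal scores over time".

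**The concern.** The concluding sentence makes a between-arm claim from a measure that exists in one arm. A gain in goal scores among coached children is an uncontrolled before-after change. It mixes any effect of coaching with the influences that the Design section says the control arm is there to account for.

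The goal measures are headed as the primary outcome measure and are the yardstick against which the secondary outcomes are checked for concordance, so they are likely to be prominent in the report. A reader planning the full trial could take a within-arm gain for evidence of benefit over printed materials.

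**Working it through.** **1. What the plan's own figure was computed for.** Inputs from Sample size: effect size 0.55, p < 0.10, power 0.80, 15 coached children. Sidedness is not stated. For change in a single group, by the normal approximation:

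n = ((z for alpha + z for power) / d)²

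| Version | Calculation | n | Power at n = 15 |
|---|---|---|---|
| One-sided 0.10 | ((1.282 + 0.842) / 0.55)² = 14.90 | 15 | 0.802 |
| Two-sided 0.10 | ((1.645 + 0.842) / 0.55)² = 20.44 | 21 | 0.686 |

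The stated 15 reproduces as a one-arm, one-sided calculation. (A one-sided t test gives power 0.784 at n = 15 and needs 16, which is close.) The formula has no control term, which agrees with the plan's wording that this is change within the intervention group.

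**2. Goal data available by arm.** Reading the schedule as one goal assessment at the first coaching session plus Times 2, 3 and 4:

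| | SFC-Peds | Control |
|---|---|---|
| Children with a goal score | up to 15 | 0 of 15 |
| Goal assessments | 15 × 4 = 60 at most | 15 × 0 = 0 |

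The 60 depends on that reading of the schedule. The zero does not.

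**3. What the comparison needs.** The between-arm difference in goal change is

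D = (mean change, coached) − (mean change, control) = Δ − c.

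The plan observes Δ and never observes c. As an illustration only, set Δ at the plan's 2-point COPM threshold and assume values for c:

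| Assumed c | −1 | 0 | 1 | 2 | 3 |
|---|---|---|---|---|---|
| D = 2 − c | 3 | 2 | 1 | 0 | −1 |

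The same coached gain fits a benefit, no difference or a disadvantage. The documents give no figure that bounds c for COPM. GAS has five levels, which limits change on any one goal to four levels in either direction, but that does not fix the sign of D. A between-arm Cohen's d on either measure has no control mean and no control standard deviation, so more children would not make it estimable.

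**4. Whether another passage supplies the missing data.** The statement that measures go to all participants at Times 1 to 4 is followed at once by the exception for goal measures. The Time 4 control survey asks about changes in health habits, and activity and diet are measured in both arms. These give indirect context but no control goal score. If the word "only" in the concluding sentence is attached to the examination of goal scores instead of to printed materials, the sentence still compares coaching with printed materials.

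**The case against.** The strongest reply is that this is one loose sentence in a plan that is otherwise clear. The secondary objective is responsiveness of measures, not efficacy. The Sample size section says feasibility studies do not assess efficacy, Data Analyses opens by ruling out inferential statistics, and the sentence speaks only of potential value. The outcome sections already say which measures serve which comparison, and an analyst with no control goal data could not compute a between-arm goal effect anyway.

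Much of this stands as a limit on the harm: the feasibility criteria are untouched, and so are the variance estimates for the full trial. It does not remove the error. A descriptive comparison also needs data from both arms, and hedged wording does not provide them. The remaining risk is the narrative conclusion, and that is what the sentence prescribes.

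Two narrower points also have force. First, since control children set no goals, c is not just missing but has no defined value under this design. The 2 − c table therefore illustrates non-identifiability and does not measure harm. Second, moving the comparison to the between-group measures could bring a new overstatement. With 15 per arm and an assumed d of 0.55, the standard error is √(2/15 + 0.55²/60) = 0.372, so the 95% confidence interval is about ±0.73. The intervals must be reported and read with that width in mind.

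**Conclusion.** The concern holds. The concluding sentence contradicts the plan's own data collection: it draws a comparison with printed materials from scores that 0 of 15 control children will have. It should be corrected, although the consequence is confined to how the secondary objective is interpreted. The finding rests on the restriction of goal measures to one arm and on no numerical assumption. The assumed values of c and the interval width at d = 0.55 are for scale only.

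**What to change.** 1. Replace the concluding sentence under Data Analyses, Secondary Objective with wording to this effect: *COPM and GAS describe change within the SFC-Peds group only and support no statement against printed materials; any such statement rests on the measures listed for between-group change, reported as between-arm differences with confidence intervals.* It would help to repeat there that the pilot does not assess efficacy.
2. As an optional clarification, say in the first sentence of that paragraph that the between-group effect sizes do not include COPM or GAS. The outcome sections already imply this.

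Collecting goal scores in control children is not proposed. The goals are created with the coach, so it would give controls part of the intervention.

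The cost is wording only, with no new data or analysis. The drawback is that the claim for the goal scores becomes less favourable, and the comparison with printed materials then depends on measures that do not score each child's own goal.

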Primary objective: To evaluate the feasibility (study design, methods, processes) and acceptability (family/child/clinician satisfaction, perceived usefulness) of conducting a RCT of a novel, brief, coaching intervention (SFC-Peds) for improving and sustaining PA and dietary habits in CWPD.

Secondary objective: To determine the responsiveness of selected outcome measures to SFC-Peds coaching over 12 months.

Principal research question: *“Is an efficacy trial to evaluate a six month SFC-Peds intervention to improve PA and dietary habits feasible to implement and acceptable to CWPD and families?”*

APPROACHES AND METHODS

Design: We will use a pilot RCT design [82] with two groups: One group (n=15) will work with a coach trained in SFC-Peds eight times over six months. The other group, the control group (n=15), will receive only standard printed materials at the start of the study. These materials will also be available to the SFC-Peds group to control for bias on study measures. The control group will allow us to control for information, maturation, repeated testing and attrition over the 12 month study [83]. All participants will receive standard care from existing clinicians who will not be delivering the SFC-Peds study intervention. The *feasibility* of trial processes, management, and resources will be assessed quantitatively. The *acceptability* of trial participation and coaching processes will be explored qualitatively. Qualitative enquiry lends insight into potential mechanisms of change and barriers to implementation and is therefore highly recommended when evaluating complex interventions [34].

Sample: Thirty children aged 10–18 inclusive and their parents who live within approximately two hours of Holland Bloorview Kids Rehabilitation Hospital (Toronto, ON) up to Thames Valley Children’s Centre (TVCC) (London, ON) will participate. The sites serve diverse socio-cultural communities.

Children and Teens in Charge of their Health: A feasibility study of solution-focused coaching to foster healthy lifestyles in children and young people with physical disabilities.

Child inclusion criteria:

- i) Between the age of 10 – 18 years inclusive
- ii) Diagnosis of SB or CP
- iii) Has physical capability to execute independent body movement with or without device
- iv) Cognitively able and willing to set PA or dietary goals
- v) Can communicate in English and respond to questions requiring some reflection and insight
- vi) Home internet connection

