Intervention Measure of Engagement – Service Provider (PRIME-SP) (see Appendix 11) and will be assessed by the coaches after each coaching session [126].

STUDY OUTCOMES AND PROCEDURES

Study Procedures

After enrollment into the study, participants will complete the following assessments at the time points outlined below (see Appendix 12 for assessment schedule). Children in the SFC-Peds group will receive the eight 60 minute coaching sessions between Time 1 and Time 2.

Assessment Timings

To assess participant retention, the feasibility study will use four assessment points over 12 months as in the planned efficacy trial: **Time 1 Baseline** (immediately preceding randomization); **Time 2** (immediately post-intervention or 6 months post-baseline for control group +/- 2 weeks); **Time 3** (three months post-intervention or 9 months post-baseline for control group +/- 2 weeks); **Time 4** (6 months post-intervention or 12 months post-baseline for control group +/-4 weeks).

Study Assessments

PRIMARY OBJECTIVE: *To evaluate the feasibility and acceptability of conducting a RCT of a novel, brief, coaching intervention (SFC-Peds) for improving and sustaining PA and dietary habits in CWPD.*

Trial feasibility will be assessed using the following pre-identified criteria (as recommended [82]):

Recruitment	2–3 participants/month recruited over 12 months (for target sample size $n=30$)	$\geq 10\%$ recruitment response rate achieved (min. feasible RCT response rate [99])
Attrition	85% participants successfully complete study (i.e. complete T1 & T4 evaluations)	75% participants complete all assessments (i.e. protocol adherence)
Adherence	Successful completers participate in $\geq 75\%$	75% of the participants complete

Children and Teens in Charge of their Health: A feasibility study of solution-focused coaching to foster healthy lifestyles in children and young people with physical disabilities.

	meetings with coach	evaluations in ≤ 2 hrs (to assess burden)
Stratification	Intervention/control groups similar for age and gender	Intervention/control groups comparable on diagnosis and functional mobility
Fidelity	High intervention fidelity (>8/10 on the Solution-Focused Fidelity Instrument [98])	Challenges/ease of remote coaching (coach, child, family report)

Trial acceptability will be explored qualitatively:

Semi-Structured Survey

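### The blinding indicator sets its cut-off at chance itself with no tolerance or interval, so chance variation alone would often put a well-blinded study on the wrong side of it

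*Combined protocol and SAP*

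**What the plan says.** The only criterion for blinding in the supplied text of the combined protocol and SAP is one clause under CHALLENGES. Assessors state which group they believe each participant is in, and "blinding success is indicated by accuracies at or below chance level". The clause does not give the value of chance, a tolerance around it, or an interval for the observed accuracy. It also does not say whether assessors may answer that they do not know. The other mention of blinding, under Randomization, concerns keeping the block size from research staff and sets no criterion.

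The Design paragraph gives 15 children in the coaching group and describes the comparator thus: "The other group, the control group (n=15), will receive only standard printed materials". A chance level of 50% follows from that split, but the plan does not state it.

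The feasibility criteria are introduced with "Trial feasibility will be assessed using the following pre-identified criteria". The table that follows covers recruitment, attrition, adherence, stratification and fidelity, and has no blinding row. Under DATA ANALYSES the secondary objective already uses "confidence intervals both within and between groups", but for effect sizes and not for guess accuracy.

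**The concern.** Under perfect blinding, observed accuracy falls on either side of 50% by chance. A cut-off placed exactly at 50% therefore splits the sampling distribution near its middle, and a study in which nobody could tell the groups apart will land above the line a large part of the time. Read literally, the plan would not indicate success for that study, although its result may be statistically indistinguishable from guessing. Reading at chance as compatible with chance avoids this, but the plan does not say what degree of departure still counts as compatible.

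At stake is how the team describes assessor blinding when it designs the full trial. Some outcomes, such as the six-minute tests, waist circumference and skinfolds, are taken by an assessor. Whether assessors stayed blind is therefore worth learning from this study, even though many other measures are child or parent report.

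**Working it through.** The plan states no figure for the blinding indicator, so there is nothing to reproduce first.

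**Inputs**
- Guesses: n = 30, one per child (Sample and Recruitment sections).
- Chance: 15/30 = 50% (inferred from Design).
- Assumptions not in the plan: each guess is forced between two groups, guesses are independent, and all are pooled.
- Possible smaller n: the attrition criterion is "85% participants successfully complete study", and 0.85 × 30 = 25.5, so 25 or 26 guesses if taken at the end.

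**Step 1. Chance of missing the cut-off under perfect blinding.** Let X be the number correct, X ~ Binomial(n, 0.5). The cut-off is missed when X > n/2.
- n = 30: P(X ≥ 16) = 0.428.
- n = 26: 0.423. n = 25, or any odd n: 0.500.
- n = 60: 0.449. n = 90 (three guesses per child, treated as independent): 0.458.

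More guesses do not help. As n grows, an exact tie becomes rarer and the probability moves towards one half.

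**Step 2. Don't-know answers.** If a share d of answers is don't-know and these count as not correct, the probability of a correct answer under perfect blinding is (1 − d)/2. P(X ≥ 16 of 30) becomes:

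| d | P(correct) | P(cut-off missed) |
|---|---|---|
| 0% | 0.500 | 0.43 |
| 5% | 0.475 | 0.32 |
| 10% | 0.450 | 0.23 |
| 20% | 0.400 | 0.10 |

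**Step 3. Assessors who lean to one answer.** With 15 children per arm and probability q of naming a given arm whatever the truth, the number correct is Bin(15, q) + Bin(15, 1 − q). P(more than 15 correct) is 0.421 at q = 0.7, 0.375 at q = 0.9, and 0 if the answer is always the same.

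**Step 4. What the misses look like.** Under the assumptions of Step 1 with n = 30, P(16 ≤ X ≤ 20) = 0.406, and 0.4064/0.4278 = 0.95 of all misses. Exact (Clopper–Pearson) 95% intervals, with limits at the Beta quantiles 0.025 of (x, n − x + 1) and 0.975 of (x + 1, n − x):
- 16/30 (53%): 34% to 72%
- 20/30 (67%): 47% to 83%
- 21/30 (70%): 51% to 85%, the first count whose interval lies above 50%

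So about 95% of the misses in a perfectly blinded study are results that are compatible with guessing.

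**Step 5. The other direction.** P(X ≤ 15 of 30), the chance that success is indicated, by true accuracy: 0.57 at 50%, 0.36 at 55%, 0.18 at 60%, 0.02 at 70%. The rule seldom passes marked unblinding. It passes slight unblinding fairly often, and it passes perfect blinding only a little more than half the time.

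**The case against.** The strongest reply has four parts.

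*The text calls nothing a failure.* It says what indicates success and is silent on 16/30. The team could report 16/30 and describe it as close to chance. DATA ANALYSES makes the feasibility assessment descriptive, and the sentence after the blinding clause sends any adaptations to a structured decision process rather than an automatic rule. This stands. A reader might infer that results above chance are uninterpretable, or that the plan would declare blinding failed. The documents support neither: such a result can be reported, but the stated rule does not distinguish it from chance variation.

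*The 43% depends on assumptions.* This also stands. The plan does not say that guesses are forced, single, pooled or independent. Step 2 shows the figure falling to 0.23 if one answer in ten is a don't-know counted as not correct, and Step 3 shows it reaching 0 when every answer is the same. The figure must be quoted with its conditions.

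*Nothing depends on the clause.* It is outside the feasibility table and feeds no estimate. This stands and keeps the point small.

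*The fix sets no margin either.* True. At this sample size an interval around 16/30 fits both good blinding and substantial unblinding. The gain is that the uncertainty is shown and not hidden behind a threshold.

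Three further readings are tempting but are not grounds here:
- Goal Attainment Scaling (GAS) and the Canadian Occupational Performance Measure (COPM) are given to the coached group alone ("Issue identification and goal attainment measures are administered to SFC-Peds participants only") and repeated by a different coach ("GAS and COPM re-assessment will be conducted by a coach who has not worked with the child"). A reader might infer that these coaches' guesses inflate accuracy. The plan does not say that they are among the assessors asked.
- The plan says "the feasibility study will use four assessment points over 12 months" and the clause names none of them for the guess. The assessment schedule is in Appendix 12, which is not in the supplied text, so the timing cannot be called missing.
- The rule has no lower limit, so systematically wrong guessing would count as success. That is a remote case and adds little.

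**Conclusion.** The concern holds in a limited form. The rule judges blinding from a point estimate against a cut-off at chance, with no tolerance. With 30 forced, independent, pooled guesses and a 50% chance level, a perfectly blinded study misses it with probability 0.43. The probability is lower if don't-know answers are counted as not correct or if assessors lean strongly to one answer, and 0.50 with an odd number of forced guesses. Most misses have intervals that include 50%, so followed literally the rule can withhold an indication of success for reasons of chance alone.

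A reader might also infer that the rule conceals unblinding. For marked unblinding it does not: at 70% true accuracy success would be indicated only 2% of the time. Materiality is low, since no tabulated criterion or planned analysis uses the result. The change is still worth making, because this clause is the only basis in the supplied text for judging assessor blinding and the correction is almost free.

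**What to change.** Replace the clause under CHALLENGES with:

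> The proportion of correct guesses by assessors of the measures given to both groups will be reported by arm and overall (by time point if repeated, with any don't-know answers shown separately) with exact 95% confidence intervals, and compared with 50%; blinding success will not be judged from the point estimate alone.

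Two notes on use. The 50% comparator applies to definite answers, which is why don't-knows are shown apart. The two arms should be read together, because a lean to one answer raises accuracy in one arm and lowers it in the other.

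The cost is about one sentence on a question already being asked, with no added visit or measure, and it suits a plan that already reports confidence intervals for effect sizes. The downside is width. With about 30 guesses, 15/30 gives 31% to 69%, and intervals by arm are wider still, so the study can rule out only marked unblinding and the conclusion will be more cautious. The interval should not become a new pass/fail test. It would lie wholly above 50% (21 or more of 30) in only 18% of studies with 60% true accuracy and 59% of studies with 70%, so an interval that includes 50% is not proof of blinding.
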